5.2 Inclusion Criteria

Women must meet all the following criteria to be eligible for inclusion in the study. Any exclusionary laboratory values can be repeated at a later date within the

screening window. If the repeated laboratory values meet inclusion criteria, then the participant can be enrolled. If there is concern that the participant's health status has changed between the screening visit and the enrollment visit or if there is a clinical concern by the study investigators, the screening laboratories can be repeated prior to enrollment.

- 1) Age 18 through 45 years (inclusive) at screening
- 2) Able and willing to provide written informed consent and take part in the study procedures
- 3) Able and willing to provide adequate locator information, defined as at least two other alternate contacts
- 4) HCV antibody seropositivity with detectable HCV RNA viral load at screening
- 5) Chronic HCV infection of at least 6 months by laboratory report or participant reported medical history as determined by the site PI/designee, or if duration of HCV cannot be determined then the participant can be enrolled if there is no clinical evidence of acute hepatitis C infection (defined by CDC as presence of jaundice or total bilirubin >/= 3.0 mg/dL/51 μmol/L or ALT >200IU/L)
- 6) Singleton pregnancy at 20 + 0 to 30 + 0 weeks' gestation at enrollment with gestational dating confirmed by ultrasound
- 7) Having a comprehensive anatomy scan with no evidence of major structural abnormalities as defined by the CDC birth surveillance toolkit (https://www.cdc.gov/ncbddd/birthdefects/surveillancemanual/chapters/chapter-4/chapter4-1.html) or an anomaly that would significantly impact delivery timing or neonatal outcomes as determined by the Protocol Safety Review Team (PSRT) prior to enrollment
- 8) Documented negative Hepatitis B testing for current infection (negative HBsAg test) prior to enrollment
- 9) If living with HIV, must be on antiretroviral therapy with HIV viral load <50 copies/mL/40 IU/mL on the most recent HIV viral load test within 30 days before enrollment and agree to continue antiretroviral therapy throughout study participation
- 10) If taking acid-suppressant medication(s), willing and able to either discontinue administration during the 12-week period of study treatment or to follow specific dosing instructions for concomitant use with SOF/VEL
- 11) Per participant report at screening and enrollment, agrees not to participate in other research studies involving investigational medications or investigational medical devices for the duration of study participation (does not include duration of infant participation). Note: maternal participants can participate in research studies that include standard of care medications.

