3 OBJECTIVES AND ENDPOINTS

3.1 Primary Objectives:

1. To evaluate the sustained virologic response 12 weeks after completion of SOF/VEL treatment (SVR12) in women treated during pregnancy.

2. To evaluate impact of antenatal treatment with SOF/VEL on the gestational age at delivery for women who received SOF/VEL for HCV treatment during pregnancy.

3.2 Primary Endpoints:

- Maternal HCV RNA PCR 12 weeks after completion of SOF/VEL treatment (HCV RNA PCR below the lower limit of quantification will be considered evidence of SVR12)
- 2. Preterm delivery (spontaneous and iatrogenic) prior to 37 weeks' gestation

3.3 Secondary Objectives:

- 1. To evaluate the maternal safety of HCV treatment during pregnancy with SOF/VFI
- 2. To evaluate the neonatal safety of HCV treatment during pregnancy with SOF/VEL
- 3. To determine the rate of HCV perinatal transmission among women treated with SOF/VEL during pregnancy according to HIV co-infection status

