7.2 Visit 1- Screening (V1)

Potential participants will be encouraged to speak with their primary care/OB provider to determine whether to initiate HCV treatment during pregnancy before enrolling in the study.

Written informed consent will be obtained before any screening procedures are initiated. Screening can take place anytime within the screening gestational age window (12+0 to 29+6 weeks) with gestational age being determined by available clinical information and confirmed by ultrasound prior to enrollment. The screening visit questionnaire will include information about the diagnosis of HCV, any past or ongoing HCV risk factors, and any past HCV care or treatment. If an anatomy ultrasound has not been performed by the time of the screening visit, then it should be performed prior to enrollment as part of routine obstetric care. The study team may assist the participant in scheduling this ultrasound. Multiple visits may be needed to complete all required screening procedures as necessary.

The actual screening visit may occur anytime during the protocol defined screening window of 12+0 to 29+6 weeks. Routine clinical care laboratory values collected up to 4 weeks prior to the **date of the screening visit** may be used for screening purposes. In this case, any STORC screening required laboratory tests that were not done as part of clinical care within 4 weeks should be drawn at the time of the STORC Screening Visit. Any exclusionary laboratory values can be repeated at a later date within the screening window. If the repeated laboratory values meet inclusion criteria, then the participant can be enrolled. If there is concern that the participant's health status has changed between the screening and the enrollment visit or if the study investigators have concerns about the woman's health status, the screening laboratories can be repeated prior to enrollment.

Table 3: Screening Visit (V1)

Table 3: Screening Visit (V1)					
Visit 1- Screening Visit Component Procedures					
Component					
Administrative and Regulatory	 Assess eligibility Review and obtain written informed consent ICF Comprehension Assessment Assign participant ID (PTID) Sign appropriate medical record releases (i.e. to obtain records from prenatal care and outside records as necessary) Collect locator information Collect demographic information Visit questionnaire Provide reimbursement for study visit Schedule next visit 				

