Clinical	 Collect medical history & review and print medical/prenatal records including documentation of previous hepatitis C treatment, if applicable Review and obtain documentation of previous liver biopsy, liver imaging and/or noninvasive measures of fibrosis, if applicable Collect concomitant medications Perform full physical examination, including Fetal Heart Tones (FHTs) Confirm gestational dating (by available clinical information but must be confirmed by ultrasound prior to enrollment) 				
Local Laboratory Tests	 Collect blood: Complete blood count (CBC) with differential and platelets* HCV antibody and RNA viral load* HCV genotype (if not available) Hepatic function panel (AST, ALT, albumin, total and direct bilirubin, alkaline phosphatase)* Creatinine/eGFR * If living with HIV, perform HIV RNA PCR (viral load) if not done within 30 days of screening and CD4 cell count if not done within 6 months of screening*** Hepatitis B virus testing (HBsAg, anti-HBc, anti-HBs) if not done as part of routine prenatal care PT/INR* Lipase* Creatine kinase* 				

^{***}If greater than 30 days between screening and enrollment, HIV RNA PCR must be repeated/available and within eligibility criteria to enroll

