7.3 Visit 2- Enrollment (V2)

The following procedures will occur at the enrollment visit (V2). The visit questionnaire includes any changes in the participant's medical history and any new or ongoing HCV risk factors. During the enrollment visit the participant will be given instructions on taking the study medication.

^{*}Results of routine clinical care laboratory testing conducted within 4 weeks of screening visit date may be used towards the screening visit.

Table 4: Enrollment (V2)

Enrollment Visit 2 (V2)		
Component Procedures		
Administrative and Regulatory	 Confirm eligibility Review/update locator information Visit Questionnaire Provide counseling regarding protocol adherence Provide reimbursement for study visit Schedule next visit 	
Clinical	 Review/update medical history Review/update concomitant medications Document pre-existing conditions Perform modified physical examination, including FHTs 	
Study Medication	 Provide instructions regarding study medication/daily use Provide study medication and observe first dose (day 1) of medication in office 	
Local Laboratory Tests	 Collect blood: HCV RNA viral load Blood sample for HCV genomic deep sequencing (collected but only used in the case of treatment failure) or stored sample for future use, as applicable If living with HIV and more than 30 days between screening and enrollment, HIV RNA PCR must be repeated prior to enrollment (if a clinical HIV viral load within 30 days of enrollment is not available) 	

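### SVR12 can be credited to women with no quantifiable HCV RNA at the first dose, because the evaluable definition has no baseline-viraemia condition

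*Protocol*

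**What the plan says.** **Entry.** Inclusion criterion 4 (5.2) asks for "HCV antibody seropositivity with detectable HCV RNA viral load at screening". The threshold is detectable, not quantifiable, and the time is screening. Criterion 5 asks for at least 6 months of infection by laboratory report or reported history, but adds: "if duration of HCV cannot be determined then the participant can be enrolled if there is no clinical evidence of acute hepatitis C infection".

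**Age of the qualifying result.** Section 7.2 sets the screening window: "Screening can take place anytime within the screening gestational age window (12+0 to 29+6 weeks". It also accepts older results: "Routine clinical care laboratory values collected up to 4 weeks prior to the" screening visit. In Table 3 the line "HCV antibody and RNA viral load" carries the asterisk for this allowance. Enrolment and the first dose may be as late as 30+0 weeks (5.2, Table 1).

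**Visit 2.** Table 4 (7.3) lists an HCV RNA viral load and, at the same visit, "Provide study medication and observe first dose (day 1) of medication in office". It does not say which comes first, and no eligibility or analysis rule uses the V2 result.

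**Success and analysis set.** Section 3.2 states: "HCV RNA PCR below the lower limit of quantification will be considered evidence of SVR12". Sections 10.1 and 7.4.4 make a woman evaluable if she has a viral load from V6 or later. A woman without one is replaced. Neither section mentions RNA at baseline.

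**The concern.** Primary objective 1 is virologic response to treatment. The study has one arm, so nothing separates the drug's effect from RNA that was already below LLOQ when dosing began.

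There are two ways in. A result can be detectable but below LLOQ, which satisfies entry while lying on the success side of the endpoint threshold. Or a woman may be viraemic at screening and no longer so at the first dose. The unknown-duration route in criterion 5 does not rule out recent infection without clinical signs.

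The error runs one way. The SVR12 test is one-sided and looks for a shortfall from 97%, so failing to reject is the reassuring result, and near-automatic successes push towards it. The perinatal transmission rate (secondary objective 3) shares the weakness, since its mothers are the same women.

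**Working it through.** **1. Longest gap from qualifying RNA to first dose.** Inputs: earliest screening 12+0, look-back 4 weeks (7.2, Table 3 footnote), latest first dose 30+0 (5.2).

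- RNA drawn at screening: 30 − 12 = 18 weeks.
- RNA from earlier clinical care: 30 − (12 − 4) = 22 weeks.

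Both are extremes, not typical values. For comparison, an HIV RNA older than 30 days must be repeated before enrolment (Tables 3 and 4). Repeating the screening HCV RNA is optional.

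**2. The protocol's own power figure (10.3).** Inputs: n = 100, null SVR12 97%, alternative 92%, one-sided nominal 10%. Let F be the number of failures.

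- P(F ≥ 5 | 100, 0.03) = 0.182, above 0.10, so not allowed.
- P(F ≥ 6 | 100, 0.03) = 0.081. The test rejects at 94 or fewer successes.
- P(F ≥ 6 | 100, 0.08) = 0.820.

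The stated 82% is reproduced.

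**3. Effect of k women below LLOQ at first dose.** The documents give no k; I assume 1, 3, 5 and, as a stress case, 10. Treat all k as successes (an upper bound) and take true SVR12 as 92% in the rest.

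- Expected SVR12 = [k + 0.92 × (100 − k)] / 100
- Power as written = P(F ≥ 6 | 100 − k, 0.08)

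| k | Expected SVR12 | Rise | Power as written |
|---|---|---|---|
| 0 | 92.0% | 0 | 82.0% |
| 1 | 92.1% | 0.1 points | 81.3% |
| 3 | 92.2% | 0.2 points | 79.7% |
| 5 | 92.4% | 0.4 points | 78.1% |
| 10 | 92.8% | 0.8 points | 73.5% |

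**4. Does excluding them change the test?** Find the smallest c with P(F ≥ c | n, 0.03) ≤ 0.10.

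| n | P(F ≥ 5), null | P(F ≥ 6), null | c | Power at 92% |
|---|---|---|---|---|
| 99 | 0.177 | 0.078 | 6 | 81.3% |
| 97 | 0.167 | 0.072 | 6 | 79.7% |
| 95 | 0.157 | 0.067 | 6 | 78.1% |
| 90 | 0.134 | 0.054 | 6 | 73.5% |

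The critical value stays at 6 failures down to n = 82. The excluded women contribute no failures and the cut-off does not move, so the decision and the power match step 3. Only the estimate is corrected.

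**5. Exclusion with replacement.** With 100 viraemic women the calculation is again step 2: 82.0%.

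**The case against.** **The effect is small and its frequency unknown.** This stands. No passage shows that any such woman will be enrolled, and criterion 5 first asks for 6 months of infection. The case rests on what the endpoint means, not on a large bias.

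**The protocol already has safeguards.** Section 2.5 says the screening RNA is meant to confirm active infection, screening laboratories can be repeated if health status may have changed, eligibility is confirmed at V2, and exclusion 8 covers conditions that would complicate interpretation. All true, but repeating and excluding are left to the site's judgement, and none requires RNA at or above LLOQ at the first dose.

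**Analysis sets belong in the SAP.** Often so, and an unseen SAP may add a restriction. But sections 10.1 and 7.4.4 themselves define who is evaluable, and 7.4.4 ties replacement to it. That rule is in the protocol and is incomplete as written.

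**Stronger readings to avoid.**

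- A reader might infer that a woman detectable but below LLOQ at entry has already met the primary endpoint untreated. She has not: the endpoint is measured 12 weeks after treatment ends, and her RNA could be quantifiable by then. Counting all k as successes is therefore an upper bound.
- A reader might take the fall in power from 82% to 78% as a loss that exclusion would repair. Steps 3 and 4 show that exclusion alone recovers none of it.
- A reader might assume the V2 sample is already pre-dose. Table 4 gives no order.
- A reader might conclude that transmission should be analysed only in V2-viraemic mothers. The 4–7% comparator is described in 2.1 as the risk in infants of women with HCV, and the documents do not show whether restriction would improve or harm comparability.

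**Conclusion.** The point holds as a gap in the definition of the SVR12 analysis set. Entry uses detectable RNA at screening, success uses LLOQ after treatment, and nothing requires RNA at or above LLOQ when dosing starts. A woman below LLOQ at the first dose and at V6 is recorded as cured of viraemia that was not quantifiable.

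The size is small: at most about 0.1 to 0.4 points on SVR12 for 1 to 5 such women per 100, always towards treatment. This rests on an assumed k, on 92% response in the others, and on every such woman counting as a success. The test decision does not depend on whether they are excluded without replacement. For transmission no size can be given. The change is worth making because it improves the meaning of a primary endpoint at almost no cost.

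**What to change.** 1. In 10.1 and 10.4.4, and in the matching sentence of 7.4.4, define SVR12-evaluable women as those with V2 HCV RNA at or above LLOQ and an HCV RNA result from V6 or later.
2. In 7.3 and Table 4, state that the V2 HCV RNA sample is drawn before the observed first dose.
3. Extend the existing replacement rule to women who are not evaluable under this definition, so that 100 viraemic women and 82% power are kept. Without replacement, power is 81% to 78% for k = 1 to 5.
4. Keep all treated women in the preterm-birth and safety analyses.
5. Report how many women were below LLOQ at V2, and show SVR12 and perinatal transmission both in all women and in V2-viraemic women.

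Cost: a few sentences and no new sample or visit. A few women (0 to 5 on the assumption above) may leave the SVR12 denominator or need replacing, which could lengthen accrual slightly.

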5.3 Exclusion Criteria

Women who meet any of the following criteria will be excluded from the study:

- 1) Participant report of any of the following at screening or enrollment:
 - a. Previous DAA treatment for HCV (prior interferon-based treatment is acceptable) without documentation of SVR12 (HCV RNA below the lower limit of quantification at least 24 weeks after DAA initiation)
 - Use of any medications contraindicated with concurrent use of velpatasvir or sofosbuvir according to the most current EPCLUSA® package insert³⁰
 - c. Plans to relocate away from the study site area in the next 16 months and unable/unwilling to return for study visits
 - d. History of cirrhosis documented or reported by previous liver biopsy, imaging tests or on at least 2 noninvasive laboratory tests of fibrosis, including compensated cirrhosis
- 2) Reports participating in any other research study involving investigational medications or investigational medical devices within 60 days or less prior to enrollment (does not include research studies involving standard of care medications)
- 3) Known fetal chromosomal abnormality prior to enrollment (confirmed by chorionic villus sampling or amniocentesis)
- 4) Clinically significant and habitual non-therapeutic drug use, not including marijuana, as determined by site Pl/designee at screening and enrollment
- 5) At screening and enrollment, as determined by site PI/designee, any significant, uncontrolled, active or chronic cardiovascular, renal, liver, hematologic, neurologic, gastrointestinal, psychiatric, endocrine, respiratory, immunologic disorder or infectious disease other than HCV (or HIV as outlined in eligibility criteria)
- 6) Any of the following laboratory abnormalities at screening:
 - a. Aspartate aminotransferase (AST) or alanine transaminase (ALT) greater than 10 times the upper limit of normal
 - b. Hemoglobin less than 9 g/dL (90 g/L)
 - c. Platelet count less than 90,000 per mm³ (90,000x10⁹/L)
 - d. International normalized ratio (INR) > 1.5
 - e. Creatinine greater than 1.4 mg/dL (124 μmol/L)
- 7) If living with HIV, CD4 count less than 200 cells/mm³ within 6 months of enrollment.
- 8) Any other condition that, in the opinion of the site PI/designee, would preclude appropriate informed consent, make study participation unsafe, complicate interpretation of study outcome data, or otherwise interfere with achieving study objectives.

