HCV cure provides significant health benefits outside of pregnancy. The goal of HCV treatment is to render HCV undetectable in the serum, liver tissue and mononuclear cells¹¹⁻¹³. Sustained virologic response (SVR12) is defined as the absence of detectable HCV RNA in the serum at least 12 weeks after the completion of therapy. SVR12 has been shown to be a durable predictor of HCV cure when HCV RNA is collected for five years or more^{14,15}. Patients cured of HCV experience significant health benefits including decreased liver inflammation and improvement in fibrosis and cirrhosis¹⁶. Additionally, SVR12 is associated with a 70% reduction in the risk of hepatocellular carcinoma and a 90% reduction in the risk of liver-related mortality and need for liver transplantation¹⁷. Furthermore, treatment of persons who use injection drugs can prevent ongoing transmission of HCV, or "treatment as prevention 18." For these reasons, the joint American Association for the Study of Liver Disease (AASLD) and the Infectious Diseases Society of America (IDSA) treatment guidelines recommend that all HCV-infected persons be treated 19. Despite this recommendation, pregnant women are excluded because the safety and efficacy of treatment during pregnancy has not been established.

Pregnant women are a priority population in HCV elimination efforts. In 2016, the World Health Organization (WHO) adopted the goal of eliminating hepatitis as a major public threat by 2030 by reducing hepatitis incidence from 6-10 to 0.9 million cases, and to reduce annual hepatitis deaths from 1.4 to 0.5 million²⁰. In the national response to the WHO goal, the Department of Health and Human Services National Viral Action Plan 2017-2020 specifically includes pregnant women as a priority population due to the risk of perinatal transmission²¹. Although avoidance of certain obstetric procedures, such as amniotomy and invasive fetal monitoring, may

decrease perinatal HCV transmission, evidence is lacking²². Perinatal transmission of HCV is thought to occur around the time of parturition. Thus, curative HCV treatment during pregnancy could be the most effective intervention to prevent perinatal transmission.

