2.4 Clinical Studies

2.4.1 Clinical Studies of Sofosbuvir/Velpatasvir for the Treatment of HCV

Approximately 1035 participants without cirrhosis or with compensated cirrhosis have been enrolled in several multicenter, Phase 3 trials to assess the efficacy of treatment with SOF/VEL for 12 weeks in patients with genotypes 1, 2, 3, 4, 5, and 6 chronic HCV in ASTRAL-1, ASTRAL-2 and ASTRAL-3 (Table 2). ASTRAL-1 was a randomized, double-blind, placebo-controlled trial that evaluated 12 weeks of treatment with SOF/VEL compared to placebo in participants with genotype 1, 2, 4, 5, or 6 infection without cirrhosis or with compensated cirrhosis³¹. ASTRAL-2 was a randomized, open-label trial that evaluated 12 weeks of SOF/VEL compared to 12 weeks of SOF plus ribavirin in subjects with genotype 2 infection³². ASTRAL-3 was a randomized, open-label trial that evaluated 12 weeks of SOF/VEL compared to 24 weeks of SOF plus ribavirin in genotype 3 infection³². Approximately 40% (over 400 participants) in these trials were women. There were no on-treatment virologic failures reported (persistent viremia while actively taking SOF/VEL), however 13 (1%) participants experienced virologic failure after treatment or relapse, most commonly among participants with genotype 3 infection. Another 12 (5%) participants failed to achieve SVR12 due to non-adherence, adverse reaction (n=2) or another reason for treatment interruption (Table 2).

Table 2: Virologic outcome of a 12-week course of SOF/VEL for the treatment of HCV infection in participants without cirrhosis or with compensated cirrhosis from ASTRAL-1. ASTRAL-2. and ASTRAL-3

geno-	Total n	SVR12	SVR12	on-treatment	after-treatment	Other
type		n	rate	virologic failure	virologic Failure	
1	328	323	98%	0	2 (1%)	3 (1%)
2	238	237	100%	0	0	1(<1%)
3	277	264	95%	0	11(4%)	2 (1%)
4	116	116	100%	0	0	0
5	35	34	97%	0	0	1 (1%)
6	41	41	100%	0	0	0

Safety

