6 STUDY MEDICATION

6.1 Regimen

Each participant will take a 12-week course (84 consecutive days) of SOF/VEL(400 mg of sofosbuvir and 100 mg of velpatasvir), one tablet by mouth once daily.

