7.4.4 Post-Treatment (SVR12) (V6) Visit

The following procedures will occur at the Post-Treatment (SVR12) visit (V6), which should be scheduled 12 weeks ± 4 days from the last dose of study medication. The V6 visit can occur simultaneously with the 8-week Follow-up Visit for the infant (iV1), as applicable. This is the last scheduled clinic visit specifically for the mother. If an HCV RNA test is not obtained at the V6 visit or abstracted from the medical record

^{**}Laboratory test performed as applicable for participants who deliver at site hospitals.

within the V6 visit window or later, then the participant is NOT evaluable and will be replaced with a new participant.

Table 8: Post Treatment (V6)

Visit 7 (V6) Post Treatment Visit		
Component Procedures		
Administrative and Regulatory	 Review/update locator information Visit questionnaire Provide reimbursement 	
Clinical	 Review/update medical history Review/update concomitant medications Perform modified physical examination Record/update AEs Provide available test results from delivery, as applicable 	
Laboratory	 Collect blood: CBC with platelets and differential Hepatic function panel (AST, ALT, albumin, total and direct bilirubin, alkaline phosphatase) PT/INR Creatinine/eGFR Lipase Creatine kinase HCV RNA viral load* Blood sample for HCV genomic deep sequencing (collected and only used in the case of treatment failure) or stored sample for future use, as applicable. 	

^{*}If the participant does not come to the V6 visit, then the HCV RNA viral load may be abstracted from the medical record if it occurs during the visit window or later. If the HCV RNA is detectable then every effort should be made to have the participant return for a blood sample for HCV genomic deep sequencing.

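### Exclusion 1a dates SVR12 after prior DAA treatment from the start of the course, which contradicts the protocol's own definition unless that course lasted 12 weeks

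*Protocol*

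**What the plan says.** Exclusion 1a (Protocol section 5.3) excludes women with previous DAA treatment "without documentation of SVR12 (HCV RNA below the lower limit of quantification at least 24 weeks after DAA initiation". Its clock starts with the first dose of the earlier course, and no course length is specified.

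Elsewhere the protocol counts SVR12 from the end of treatment:

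- Section 2.1 defines it as "absence of detectable HCV RNA in the serum at least 12 weeks after the completion of therapy".
- Section 3.2, the first primary endpoint, uses "Maternal HCV RNA PCR 12 weeks after completion of SOF/VEL treatment".
- Section 7.4.4 places the SVR12 visit at "12 weeks ± 4 days from the last dose of study medication".

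The study regimen lasts 12 weeks (section 6.1: "Each participant will take a 12-week course (84 consecutive days) of SOF/VEL"). The protocol also mentions a longer DAA course. Section 2.4.1 describes a cited trial that compared "12 weeks of SOF/VEL compared to 24 weeks of SOF plus ribavirin in genotype 3 infection".

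Section 5.2 requires detectable HCV RNA at screening. A DAA-experienced woman who passes 1a is therefore implicitly regarded as cured by the earlier course and since reinfected.

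**The concern.** Exclusion 1a has to separate women cured by an earlier DAA course from women who relapsed after it. Time off treatment is what separates them. In Table 2 of section 2.4.1 there were no on-treatment virologic failures. All 13 virologic failures came after treatment, 11 of them in genotype 3. A negative RNA at or soon after the last dose therefore says little about cure.

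Because the bracket counts from initiation, the off-treatment time it guarantees shrinks as the earlier course lengthens. A relapser admitted this way would be counted in a primary SVR12 comparison against 97%. If her chance of cure were lower than that, it would count against treatment in pregnancy. In the other direction, the bracket can refuse a woman with a valid SVR12 after a short course.

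No other provision reliably catches the error. Exclusion 8 lets the site investigator refuse a woman on general grounds but sets no timing rule. The sequencing in section 10.5.5 compares baseline with post-treatment samples; it does not ask whether the viraemia at entry is a relapse from an earlier course.

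**Working it through.** **Inputs.** From the protocol: 24 weeks from initiation (5.3, 1a); 12 weeks from completion (2.1, 3.2, 7.4.4); a 12-week study course (6.1); a 24-week course in a cited trial (2.4.1); the SVR12 test with n = 100, null 97%, alternative 92%, one-sided 10%, 82% power (10.3). Assumed, because the protocol does not give them: prior courses of 8 and 16 weeks, the number m of misclassified relapsers, and their cure rate q on retreatment.

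**Step 1: compare the two clocks.** For an uninterrupted prior course of L weeks, the earliest SVR12 under section 2.1 is at week L + 12 from initiation. The bracket accepts week 24 whatever L is. Off-treatment time at week 24 is 24 − L.

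| Prior course L (weeks) | Earliest SVR12, L + 12 | Off-treatment time at week 24, 24 − L | Bracket compared with section 2.1 |
|---|---|---|---|
| 8 (assumed) | week 20 | 16 weeks | 4 weeks stricter |
| 12 | week 24 | 12 weeks | same |
| 16 (assumed) | week 28 | 8 weeks | 4 weeks short |
| 24 (cited in 2.4.1) | week 36 | 0 weeks | 12 weeks short |

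The 24 weeks in 1a reproduces as 12 + 12, so it fits a course of the study's own length and no other.

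**Step 2: find who is affected.**

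- Wrong admission needs L above 12, a negative RNA at or after week 24 but less than 12 weeks after the last dose, and a later relapse. With L = 24 the window runs from week 24 to just before week 36.
- Wrong refusal needs L below 12 and no negative RNA at or after week 24. With L = 8, that is a woman whose qualifying results all fall from week 20 to just before week 24. Any later negative result satisfies 1a.
- With L of 12 or less, any RNA that meets the bracket is at least 12 weeks off treatment, so the bracket's timing cannot let a relapser in.

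**Step 3: reproduce the plan's SVR12 test.** With X cures, X ~ Binomial(100, p):

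- P(X ≤ 94 | p = 0.97) = 0.081
- P(X ≤ 95 | p = 0.97) = 0.182, above 0.10, so the test rejects at 94 or fewer
- P(X ≤ 94 | p = 0.92) = 0.820, which matches the stated 82%

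**Step 4: size the effect.** Let m of the 100 be misclassified relapsers with cure rate q and the other 100 − m have 97%. Then

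P(total ≤ 94) = Σⱼ P(Bin(m, q) = j) × P(Bin(100 − m, 0.97) ≤ 94 − j).

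With m = 1 and q = 0.70: 0.70 × P(Bin(99, 0.97) ≤ 93) + 0.30 × P(Bin(99, 0.97) ≤ 94) = 0.70 × 0.0779 + 0.30 × 0.1771 = 0.108.

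| m | q = 90% | q = 70% |
|---|---|---|
| 0 | 8.1% | 8.1% |
| 1 | 8.8% | 10.8% |
| 2 | 9.5% | 14.0% |
| 3 | 10.3% | 17.6% |

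Expected cures per 100 fall by m × (0.97 − q): 0.07 for one woman at 90%, and 3 × 0.27 = 0.81 for three women at 70%.

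**The case against.** The strongest reply is that the operative requirement in 1a is documentation of SVR12, a term section 2.1 already defines from the end of therapy. On that reading an end-of-treatment RNA after a 24-week course is not SVR12, whatever the bracket says. This is a fair reading, but the bracket is the explanation given inside the criterion itself, and a site that follows it literally commits no deviation. The two passages conflict and need reconciling.

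The remaining objections limit the reach of the point, and they stand:

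- A reader might infer that 1a, as written, does let prior DAA failures in. The protocol does not show this. Several conditions must coincide, and the site must then accept her. Records of earlier treatment are collected at screening (Table 3), so course dates may be visible, and exclusion 8 is a partial, discretionary safeguard.
- A reader might infer that true SVR12s after short courses are generally refused. They are not, since any negative RNA at or after week 24 is accepted.
- The only longer course in the protocol is a comparator arm of a cited trial. It says nothing about how often candidates at these sites had such a course.
- The protocol gives no cure rate for retreatment after DAA failure, so a lower rate for such women is an assumption.

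**Conclusion.** The textual contradiction is certain. Exclusion 1a agrees with sections 2.1, 3.2 and 7.4.4 only for a 12-week prior course, and it does not restrict itself to such courses. The direction that matters is a prior course longer than 12 weeks, where a later relapser could be admitted as cured and reinfected. For shorter courses the bracket is only stricter.

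The consequence is uncertain and probably very small. With 1 to 3 such women among 100 and assumed cure rates of 90% to 70%, the chance of wrongly concluding that SVR12 is below 97% is between 8.8% and 17.6%, against 8.1% with none. Those figures assume that all other participants have a true rate of 97%. It would go too far to call this a demonstrated threat to the primary SVR12 test, because neither the number of such women nor their cure rate is in the protocol.

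Severity is minor. High confidence applies to the contradiction, not to its consequences.

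**What to change.** Reconcile the bracket in exclusion 1a with the protocol's own SVR12 definition, so that the interval is counted from completion of the prior DAA course.

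For women already enrolled with prior DAA treatment, check the treatment records collected at screening (Table 3) against that definition and flag any who do not meet it. Report a sensitivity analysis of SVR12 without the flagged women, with the exact binomial critical value recalculated for the smaller denominator.

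The cost is one line in an amendment, a record check on what are probably few women, and one extra analysis. No visits, samples or participants are added.
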